2.2.1. Schedule of Assessments

The schedules of study assessments and pharmacokinetics sampling schedule are presented in APPENDIX 1 and APPENDIX 2 of Protocol below

(b) (4)

(b) (4)

(b) (4)

(b) (4)

(b) (4)

(b) (4)

(b) (4)

2.3. Determination of Sample Size

The sample size chosen for this study was selected without statistical considerations. It has been determined adequate to meet the study objectives. Patients who withdraw from the study may be replaced on a case-by-case basis after discussion and agreement with the Sponsor's Medical Monitor.

Up to approximately 24 to 32 patients are planned to be enrolled into this study if all cohorts are completed. Each of the (up to) 4 cohorts will comprise up to 6-8 patients to ensure there are a minimum of 3 patients \leq 10 years of age per cohort. Patients who discontinue the study before the Week 5 treatment and evaluation period may be replaced at the discretion of the Sponsor, if discontinuation was not due to a dose-limiting toxicity (DLT).

2.4. Randomization

This is an open-label study, but the study will utilize a randomization and trial supply management (RTSM) application built within the EDC platform to unify randomization, trial supply and EDC. Each patient will be provided a unique 6-digit patient ID number. The first three digits will represent the site number and the last three digits will represent the patient number at the site. The patient ID number will remain the same for both screening and randomization. In the event a cohort has not completed the enrollment criteria of at least 3 patients \leq 10 years of age, patients $>$ 10 years of age can be stratified into a higher cohort as long as the dose escalation review has been completed and approved.

2.5. Blinding

This is an open-label study. Therefore, no blinding is applicable.

3. DATA ANALYSIS CONSIDERATIONS

The statistical analyses will be performed by Quartesian Clinical Research, using SAS Version 9.3 (or higher). All Tables, Listings and Figures (TLFs) will be produced in landscape format. In general, all data will be listed by the patient, cohort, and visit/timepoint, but not limited only to these variables. The number of variables presented in each listing can vary. Please refer to Mock tables, listings, and figures.

Data will be summarized by cohort and by RZ358 pooled treatment. The total number of patients in the study group (N) under the stated population will be displayed in the cohort header of summary tables.

Data will be summarized using descriptive statistics for continuous variables. Unless otherwise stated, descriptive statistics will include Number of patients (n), Mean, Standard Deviation (SD), Standard Error (SE), Minimum, Median, Maximum, and confidence interval (for efficacy parameters only). First Quartile (Q1) and Third Quartile (Q3) will also be included for duration (absolute time) parameters. Area over the curve (AOC) and area under the curve (AUC) of glucose will also include coefficient of variation (CV %), Geometric Mean, Geometric CV (%). In case of n=1, where n

indicates the number of evaluable patients at the particular time point, only n, mean, minimum and maximum will be displayed. The statistic “Missing” will also be evaluated by enumerating the number of missing entries/patients, if any at that visit, and presented as a summary statistic only for the available time points.

In summary tables of categorical variables, counts and percentages will be used. The count [n] indicates the actual number of patients with a particular value of a variable or event, which should always be less than or equal to the total number of patients in the respective cohort [N].

Decimal Precision Convention: The minimum and maximum statistics will be presented to the same number of decimal places as the raw data. The mean, median, Q1, Q3, Confidence interval (CI) for mean and proportion will be presented to one more decimal place than the raw data, whereas the standard deviation (SD), Standard Error (SE), coefficient of variation (CV %), Geometric Mean, and Geometric CV (%) will be presented to two more decimal places than the raw data.

The number and percentage of patients with missing values for a variable/category/event will also be presented for the resulting visits/time points under the “Missing” category. Percentage will be obtained by: % = $(n/N) * 100$. Unless otherwise stated, all percentages will be expressed to one decimal place. P-value will be presented three decimal places or P-value closer to zero will be presented as <0.001 and p-value closer to one will be presented as >0.999.

The following conventions will be applied to analyses/data presentation:

All dates will be displayed in DDMMYY format.

Unscheduled data for assessments that are specific to a discrete visit (rather than continuously measured e.g., SMBG or CGM) will be presented in Listings but not in Tables and Figures, unless missing data imputation rules (windows) are met, as described below.

Prior to implementing protocol version amendment 5.0, three patients in Cohort 1 were enrolled and treated under protocol version amendment 4.0, which differed from version 5.0 in dosing regimen (frequency) so, the following visit mapping will be followed for efficacy analysis, considering the dosing period:

“Subjects who were enrolled in Cohort 1 under protocol version amendment 4.0, their Week 1 and Week 2 data are aggregated and reported under '2 Weeks' timepoint. Similarly, Week 3, Week 4 and Week 5 data are aggregated and reported under '4 Weeks', their Week 6 and Week 7 are aggregated and reported under '6 Weeks', their Week 8 and Week 9 data are aggregated and reported under '8 Weeks/EOT' timepoint.”

Handling of Missing Data

If the Adverse Event Relationship flag is missing, the relationship for adverse event will be imputed and will be considered as “Related”. If the Adverse Event Severity grade is missing, the severity will be imputed and will be considered as “Severe”. To handle missing or partial AEs and concomitant medication dates, the following rules will be applied.

For partial AE/CM Onset/Start Date:

1. If the year is unknown, then do not impute the date but assign a missing value.

Missing day and month

If the year is same as the year of first day on study medication, then the day and month of the start date of study medication will be assigned to the missing fields.

If the year is prior to the year of first day on study medication, then December 31 will be assigned to the missing fields.

If the year is after the year of first day on study medication, then January 1 will be assigned to the missing fields.

Missing month only

Treat day as missing and replace both month and day according to the above procedure.

Missing day only

- i. If the month and year are same as the year and month of first dose date of study medication, then the start date of study medication will be assigned to the missing day.
- ii. If either the year is before the year of the first dose date of study medication or if both years are the same, but the month is before the month of the first dose date of study medication, then the last day of the month will be assigned to the missing day.
- iii. If either the year is after the year of the first dose date of study medication or if both years are the same, but the month is after the month of the first dose date of study medication, then the first day of the month will be assigned to the missing day.

For AE Stop Date:

If the stop date is complete and the imputed start date as above is after the stop date, the start date will be imputed by the stop date.

If the stop date is incomplete, no imputation needed.

For CM End Date:

CM end date will not be imputed if CM ongoing is checked.

1. If the year is unknown, then do not impute the date but assign a missing value.
2. If the month is unknown, then assign “December.”
3. If the day is unknown, then assign the last day of the month.

If AE onset date is non-missing and is before the first dose date then the AE is considered to be prior treatment.

If AE onset date is non-missing and is occurred on the same date as the first dose with the event marked as start prior to first dose of study drug on the CRF then the AE is considered to be prior treatment.

If AE onset date is missing and is marked as start prior to the first dose of study drug on the CRF then the AE is considered to be prior treatment.

If CM start date is taken prior to the first dose of study drug regardless continuing to take the medication while on study treatment, then the CM is considered to be prior treatment.

Missing data imputation for Visit-Specific Assessments (e.g., safety labs, vital signs, hepatic ultrasound, 12-lead ECG):

An unscheduled assessment (full visit or partial assessment) that is discrete and associated with a specific visit will be imputed as the scheduled assessment for the nearest visit where the applicable assessment is missing. Unscheduled data collected prior to the first dose will be assigned to the nearest missing screening visit or assessment (instead of nearest post-treatment visit). Unscheduled data collected after the final dose will be assigned to the nearest missing treatment or post-treatment visit or assessment. When an unscheduled assessment represents a value that is repeated (to a scheduled value, i.e., no missing data), then these will be adjudicated by medical review prior to database lock, to determine the value for the scheduled summary. If the unscheduled/repeat value affirms the legitimacy of the original value, the original value will be used and the unscheduled/repeat value will be additionally included in listings. When the value refutes the legitimacy of the original value

(suggesting spurious original value), the unscheduled/repeat value will be imputed to that scheduled visit, and the original value will be excluded from the dataset and listings.

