6.3.8 Electrocardiograms

During the study, 12-lead ECGs will be performed at the time points designated on the [Schedule of Assessments](#).

The patient must be in a supine position in a rested and calm state for at least 5 minutes before the ECG is conducted. If the patient is unable to be in the supine position, they should be in the most recumbent position possible. All ECGs should be performed in a standardized method, prior to blood draws or other invasive procedures. Each ECG must include the following measurements: QRS, QT, corrected QT, RR, and PR intervals, as well as an overall interpretation.

The Principal Investigator (PI) or designated site physician will review and sign all ECGs. Results must be summarized in writing and classified as normal; abnormal; abnormal, clinically significant; or abnormal, not clinically significant. Once signed, the original ECG tracing will be retained with the patient's source documents. At the request of the Sponsor, a copy of the original ECG will be made available. Unscheduled ECGs may be performed if there is a change from baseline or as deemed necessary by the Investigator.

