The 12-lead ECG measurements will include heart rate (bpm), QRS (msec), QT (msec), corrected QT (msec), RR (msec), and PR (msec) intervals, as well as an overall interpretation.

Actual and change from baseline value of quantitative ECG parameters will be summarized using descriptive statistics (n, Mean, SD, Median, Minimum, and Maximum) by visit, cohort and RZ358 Total (pediatric and adult patients) for safety population.

Overall assessment of safety ECGs (Normal, Abnormal - NCS, Abnormal – CS) will be summarized using frequency counts and percentage by visit, cohort and RZ358 Total for safety population. In addition, a shift table comparing overall interpretation (Normal, Abnormal - NCS, Abnormal - CS) of the ECG parameters at baseline vs treatment-emergent post-baseline (worst treatment-emergent category) will also be presented by cohort for safety population. For categorical shift summaries, any available pre-treatment values (screening or pre-treatment baseline) may be used to define baseline, for the categorical assignment.

Individual data listings of ECG results along with the Investigator-identified ECG abnormalities will be presented for each patient.

Clinical Laboratory Data

The Clinical Laboratory test category will include assessments of Hematology, Chemistry, Urinalysis, HbA1c, ADA Blood Collection.

(b) (4)

Quantitative parameters of hematology, chemistry, and urinalysis, actual and change from baseline values at each scheduled time-point will be summarized by visit, cohort and RZ358 Total (pediatric and adult patients) using descriptive statistics (n, Mean, SD, Median, Minimum, and Maximum) for safety population. All qualitative result parameters at each scheduled time-point will be summarized by visit, cohort and RZ358 Total using frequency counts and percentage for safety population.

Additionally, comparing the changes in categorical laboratory variables from baseline (Low, Normal, and High) / (Positive, Negative) vs treatment-emergent post-baseline (worst treatment-emergent category) will be presented by cohort using a shift table for safety population. For categorical shift summaries, any available pre-treatment values (screening or pre-treatment baseline) may be used to define baseline, for the categorical assignment.

A summary table will be presented for HbA1c by visit, cohort and RZ358 Total for safety population.

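### The worst-category safety shift tables can miss unscheduled abnormal results that neither fill a missing visit nor replace a value found spurious

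*SAP*

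**What the plan says.** SAP section 3 sets a general rule for unscheduled data from assessments tied to a discrete visit; CGM and SMBG fall outside it. Such data "will be presented in Listings but not in Tables and Figures, unless missing data imputation rules (windows) are met". The part of the same section on visit-specific assessments, which names safety laboratory tests, vital signs, hepatic ultrasound and ECG as examples, then covers three situations:

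- **The scheduled assessment is missing.** The unscheduled value "will be imputed as the scheduled assessment for the nearest visit where the applicable assessment is missing".
- **A repeat affirms the scheduled value.** Then "the original value will be used and the unscheduled/repeat value will be additionally included in listings".
- **A repeat refutes the scheduled value.** Then "the unscheduled/repeat value will be imputed to that scheduled visit, and the original value will be excluded from the dataset and listings".

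SAP 7.1.8 builds several shift tables on a worst-case category. For the laboratory tables, baseline categories "vs treatment-emergent post-baseline (worst treatment-emergent category) will be presented by cohort using a shift table for safety population". For ECGs, the table compares the overall interpretation "of the ECG parameters at baseline vs treatment-emergent post-baseline (worst treatment-emergent category) will also be presented by cohort". Physical examination and hepatic ultrasound follow the same construction. For laboratory, ECG and physical examination, the baseline side may draw on any available pre-treatment value. Nothing comparable is said of the post-baseline side.

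On why extra tests are done, Protocol 6.3.8 states: "Unscheduled ECGs may be performed if there is a change from baseline or as deemed necessary by the Investigator". Protocol 6.3.6 and 6.1.5 leave unscheduled vital signs and visits to the investigator's discretion.

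**The concern.** A table labelled worst category should show the worst valid result each patient had while at risk. Unscheduled tests are not a random sample of time: some are done because the patient's state has changed or the investigator is worried. If some of them cannot reach the table, it can show a milder worst result than the patient's own listing does.

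Repeat-dose safety and tolerability is one of the three primary endpoints, it is assessed descriptively, and cohorts hold 6 to 8 patients. In tables that small, one patient in the wrong cell is visible.

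**Working it through.** The plan states no figure on this point, so the check traces each type of post-baseline unscheduled result through SAP section 3 into the tables of 7.1.8.

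| Unscheduled result | Rule in SAP 3 | Can it set the worst category? |
|---|---|---|
| (a) Nearest scheduled assessment missing | Fills that visit | Yes |
| (b) Repeat that refutes the scheduled value | Replaces it; the scheduled value is dropped | Yes |
| (c) Repeat that affirms the scheduled value | Scheduled value tabulated, repeat listed | No |
| (d) Extra result, not a repeat, nothing missing | Meets no exception; general rule applies | No |

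**When (c) matters.** The categories are coarse: Low/Normal/High or Positive/Negative for laboratory tests, and Normal/Abnormal-NCS/Abnormal-CS for the other three. A scheduled High with a still higher repeat stays High, so nothing is lost. Case (c) changes a table only if the affirming repeat crosses a category, such as Abnormal-NCS on schedule and Abnormal-CS on repeat.

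**When (d) matters.** Take a patient whose scheduled values are all Normal and present, with one High value between visits. Under SAP 3 the patient is shown as Normal to Normal. With all values used, the patient is Normal to High.

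**Direction.** Let S be the values allowed into the table and A the same values plus those in (c) and (d). S is a subset of A, so for any fixed order of severity the worst of S is never worse than the worst of A. The omission therefore acts in one direction. This holds for (c) and (d) only; replacement under (b) can move a result either way.

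**Illustrative size.** Inputs are 6 to 8 patients per cohort and 24 to 32 in total (SAP 2.3), with percentages calculated as n/N × 100 (SAP 3). For one affected patient:

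- cohort: 1/8 = 12.5% to 1/6 = 16.7%
- total: 1/32 = 3.1% to 1/24 = 4.2%

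This is the effect of a single patient. It is not an estimate of how many patients would be affected, because the documents do not give the number of unscheduled or repeat results.

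**The case against.** A reader might infer that unscheduled results are barred from every table, or that none can reach a table once a patient's scheduled data are complete. The documents support neither. The general rule carries its own exception, and route (b) operates exactly where a scheduled value exists.

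Other points in the plan's favour:

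- **Adverse event route.** Under Protocol 6.3.14.1.1, a clinically significant laboratory abnormality that needs active management is an adverse event. Protocol 6.3.14.2.1 takes in events found through examinations, laboratory tests or other assessments, and 6.3.7 sends adverse examination changes to the AE form. Treatment-emergent events are tabulated. This stands, and is strongest for physical examination. It is only partial for the rest: a shift from Normal to High, or from Normal to Abnormal-NCS, need not become an adverse event.
- **Listings and escalation.** The omitted values stay in the listings, which Protocol 7.8 says will be reviewed, and dose escalation rests on all available interim data. So a reading that safety signals are hidden, or that escalation depends on these tables, is not supported. The table could still disagree with its own listing.
- **Purpose of unscheduled ECGs.** Protocol 6.3.8 permits them and does not require them, and investigator judgement is a separate ground. The change may first have been seen on a scheduled ECG that is already tabulated. It does not follow that every unscheduled ECG captures an otherwise unseen event.
- **Scope of the rule.** SAP 7.1.8 ties the quantitative laboratory summaries to scheduled time-points but does not repeat this for the shift tables, so one could argue that those tables use everything. However, the rule in SAP 3 covers tables and figures generally and nothing in the visible text overrides it. The mock tables are not available here and part of the laboratory text is redacted; if either settles the matter, the SAP text need only be aligned with it.

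**Conclusion.** The point holds in a limited form. As written, an extra between-visit result with no scheduled assessment missing, and an affirming repeat in a worse category, cannot set the worst treatment-emergent category in the laboratory, ECG, physical examination or hepatic ultrasound shift tables. Any resulting error makes the tables look more favourable.

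The likely total effect is unknown. One affected patient is worth 12.5 to 16.7 points in a cohort and 3.1 to 4.2 points overall, assuming cohorts of 6 to 8, a total of 24 to 32, and all of those patients in the denominator. The conclusion also assumes that the general rule in SAP 3 governs the shift tables, which is the plain reading of the visible text, and that physical examination, though not among its named examples, counts as a visit-specific assessment.

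**What to change.** 1. In SAP 3, limit the exclusion of unscheduled visit-specific data to by-visit summaries and their figures.
2. In SAP 7.1.8, state that the worst-category shift tables, and the vital-sign abnormality counts based on Table 2, use all valid scheduled, unscheduled and repeat values within a stated treatment-emergent period.
3. Exclude values found spurious under the medical review in SAP 3. Calling simply for every value after first dose would bring those back.
4. State where the period ends. The SAP closes it for adverse events at the Day 42 follow-up visit, follow-up runs to Day 105, and no end is given for the shift tables.

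No new data are needed, since Protocol 6.1.5 already has unscheduled assessments captured in the database. The cost is a short SAP change and a small programming change, best made before database lock. Abnormality counts may come out slightly higher.

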4. DEFINITIONS & DERIVATIONS

Baseline: Baseline is defined as the last non-missing value (or aggregate/integrated values in the case of CGM or SMBG) prior to the first administration of the study drug, unless otherwise stated. If the assessment occurs on the same day as the first study drug administration, then the time of assessment should be compared to the time of first dose administration.

Change from Baseline: The change from baseline values will be calculated as post-baseline value minus the baseline value.

$$\text{Percent change from Baseline} = \frac{\text{Post baseline value} - \text{Baseline value}}{\text{Baseline value}} \times 100$$

(b) (4)

(b) (4)

SMBG data entered by the patient into the electronic patient diary cannot be edited retroactively by the patient. It is both the source data and the data record, so correction of potentially spurious values cannot be performed (b) (4)

listing of possible spurious values will be medically reviewed and adjudicated for exclusion from the analysis datasets prior to database lock.

Missing data for CGM or SMBG will otherwise not be imputed since it is collected continuously or semi-continuously.

Treatment-Emergent Adverse Event (TEAE): A TEAE is defined as any clinically significant event that starts or that worsens in severity (intensity or frequency) after the first dose of study drug. For purposes of this study, TEAEs for summary tabulation will be further defined as those events which occur within a period of time through the +42 days follow-up visit after the final dose of study drug. Adverse events with onset after ICF but before first dose of study drug or after last dose of study drug +42 days will be summarized and listed separately from TEAEs.

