6.3.14 Adverse Events

6.3.14.1 Safety definitions

6.3.14.1.1 Adverse Event

An AE is any untoward medical occurrence (i.e., any unfavorable and unintended sign [including abnormal laboratory findings], symptom or disease) in a clinical study patient, which is either new in onset or pre-existing but worsened in severity or frequency, whether or not it has a causal relationship to the study investigational (medicinal) products or procedures. This includes events with onset from the time of providing written informed consent for participation in the study until the end of study visit, as defined in the protocol. Therefore, an AE may or may not be temporally or causally associated with the use of a medicinal (investigational) product.

(b) (4)

A clinical laboratory AE is any clinically significant laboratory abnormality that suggests a disease and/or organ toxicity and is of a severity, which requires active management, (i.e., change of dose, discontinuation of study product, more frequent follow-up or diagnostic investigation). (b) (4)

A treatment-emergent AE (TEAE) is defined as any clinically significant event that is not present before exposure to study drug or any event already present that worsens in either intensity or frequency after exposure to study drug.

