6.3.14.2.2 Adverse Event Severity Grading

The severity of AE will be assessed by the Investigator and graded according to the NCI Clinical Trial Classification for Adverse Events (CTCAE). Event terms not listed in the NCI-CTCAE will be evaluated using the following grading scale (see [Table 6](#)).

Table 6: Grading Scale (Terms Not Listed in NCI-CTCAE)

Term	Definition
Grade 1, Mild	Signs or symptoms easily tolerated and generally not causing interference with normal activities; of little concern to the patient and of little or no clinical significance; is not expected to have any effect on the patient's health or well-being; may or may not require medical intervention
Grade 2, Moderate	Causes interference with some usual activities; experience is of some concern to the patient's health or well-being; may require medical intervention
Grade 3, Severe	Causes interference with most regular activities; experience is of definite concern to the patient and/or poses substantial risk to the patient's health or well-being; likely to require medical intervention
Grade 4, Life-threatening	The patient was at immediate risk of death from the experience, as it occurred
Grade 5, Death	The event resulted in death (but death is not an AE)

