7.1.8. Safety Analysis

The analysis of primary safety endpoints will include assessments of AEs, vital signs, 12-lead ECGs, infusion-site observations, physical examination, hepatic ultrasound results, and clinical laboratory evaluations including glucose values. All safety analyses will be performed using the Safety Population.

Adverse Events:

Adverse Events will be coded using (MedDRA version 25.0 Mar 2022) AE coding system for the purpose of summary tables. Treatment-emergent adverse events (TEAE) will be summarized by cohorts and RZ358 Total and AEs that are non-TEAE will be identified.

For each cohort, AEs will be summarized with frequency count and percentage by MedDRA SOC and PT, with all patients treated in that cohort as the denominator, unless otherwise specified. In addition, AEs will also be summarized by severity and relationship to study drug.

All AEs and TEAEs during the study will be summarized for the respective cohorts. A patient experiencing the same AEs and TEAEs multiple times will be counted only once for that PT. Similarly, if a patient experiences multiple AEs and TEAEs (preferred terms) within the same SOC then that patient will be counted only once for that SOC. When summarizing by severity, the event with highest severity will be counted. All AEs will be listed in chronological order of the events occurred.

For purposes of this study, TEAEs for summary tabulation will be further defined as those events which occur within a period of time through the +42 days follow-up visit after the final dose of study drug. Adverse events with onset after ICF but before first dose of study drug or after last dose of study drug +42 days will be identified separately from TEAEs.

Summary tables of the following AEs will be provided:

An overview of TEAE summary will be presented by cohorts, and it will include:

- Number of Subjects with any TEAEs
- Number of subjects with any TEAEs related to study drug
- Number of subjects with any TEAEs leading to treatment/study discontinuation
- Number of subjects with TEAEs by maximum severity grade
- Number of Subjects with any serious TEAEs
- Number of Subjects with any serious TEAEs related to study drug
- Number of Subjects with any serious TEAEs leading to treatment/study discontinuation
- Number of Subjects with any serious TEAEs leading to death

➤ Number of subjects with any non-TEAEs

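### The TEAE definition requires clinical significance without saying how it is judged, so some post-dose adverse events could be left out of the TEAE tables

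*SAP*

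**What the plan says.** The protocol starts broadly: "An AE is any untoward medical occurrence" (6.3.14.1.1). Section 6.3.14.2.1 requires every identified AE to be recorded whatever its seriousness, severity or presumed cause. Clinical significance first enters as a threshold for laboratory findings: "A clinical laboratory AE is any clinically significant laboratory abnormality that suggests a disease and/or organ toxicity", and the same sentence ties it to a need for active management.

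The qualifier then reappears in the definition of treatment emergence: "A treatment-emergent AE (TEAE) is defined as any clinically significant event that is not present before exposure to study drug". SAP section 4 carries it over: "A TEAE is defined as any clinically significant event that starts or that worsens in severity". The SAP's next sentence narrows TEAEs further, for tabulation, to events through the +42-day follow-up visit.

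Severity is graded by NCI-CTCAE. For terms that NCI-CTCAE does not list, the protocol's Table 6 applies, and its Grade 1 includes events "of little concern to the patient and of little or no clinical significance" (6.3.14.2.2). The TEAE overview in SAP 7.1.8 includes the row "Number of subjects with TEAEs by maximum severity grade".

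**The concern.** Repeat-dose safety and tolerability is a primary endpoint (Protocol 2.1, SAP 5.1). In SAP 7.1.8, the overview and the tables by system organ class, relatedness, discontinuation and grade 3 or above are all built on the TEAE flag. That flag should follow from the AE record and the dosing dates. Here it also depends on a judgement that the plan neither defines nor assigns to anyone, so two programmers working from the same data could flag different events.

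The phrase is not obviously empty in this SAP. Clinically significant and not clinically significant are formal result categories (CS and NCS) for ECG, physical examination and hepatic ultrasound. A reader could reasonably apply the words in the TEAE definition as a filter. The events at risk would be the milder ones, which bear on tolerability.

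**Working it through.** The plan gives no figure to reproduce, and the size of the effect cannot be calculated. The check sets the rules side by side.

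1. **What is recorded.** Under Protocol 6.3.14.1.1 and 6.3.14.2.1, any untoward occurrence of any severity is recorded. The only visible significance threshold on becoming an AE is the one for laboratory findings.

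2. **What is counted.** Under SAP section 4, a TEAE must be (a) clinically significant, (b) new or worse after the first dose, and (c) inside the +42-day window. Condition (c) is added to (a) and does not replace it. In the protocol sentence the qualifier sits on new events, and the clause on worsening refers to any event already present. The SAP sentence places the qualifier over both. Protocol 7.1 lets the SAP supersede the protocol on analysis.

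3. **How the flag would be derived.** The visible attributes recorded per event (Protocol 6.3.14.2.1) are term, dates, severity, causality, seriousness, action taken and outcome. None of them is clinical significance. SAP section 3 imputes missing severity as severe and missing relationship as related, but has no rule for significance. So either the words are ignored and the flag is set by date, or someone makes a judgement that the visible plan does not describe.

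4. **Test cases after dosing and inside the window.**
   - A physical-examination change classed abnormal NCS: Protocol 6.3.7 sends any adverse change from baseline to the AE form, so it is an AE. Read literally, it is not a TEAE.
   - A term not in NCI-CTCAE, rated Grade 1 on Table 6: if judged to have no clinical significance, it is literally not a TEAE, although the severity row expects TEAEs by grade.
   - A Grade 1 event with an NCI-CTCAE term: nothing in the documents says that it lacks clinical significance, so its status depends on the undefined judgement.

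5. **Where an omitted event goes.** SAP section 4 and SAP 7.1.8 describe the separately reported group by onset only: after consent but before the first dose, or more than 42 days after the last dose. An in-window event judged not significant belongs to neither group. It stays in the all-AE summary and the by-patient listing. The all-AE summary is a different set, however. AE collection runs from consent to the Day 105 visit, so the summary also takes in pre-dose events and a further 105 − 42 = 63 days of nominal follow-up.

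6. **Size.** The documents give no expected share of Grade 1 or NCS events. The lower bound is zero (flag set by date). The upper bound is every in-window AE that someone judges not clinically significant, and no number can be put on it.

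**The case against.** A reader might infer that the trial defines Grade 1 as lacking clinical significance, so that mild events disappear from every TEAE table. The documents do not support that. Table 6 is a fallback for terms outside NCI-CTCAE. Its wording allows for little significance as well as none, so even a Table 6 Grade 1 event is not excluded by definition. SAP 7.1.8 tabulates TEAEs by maximum grade with no lower cut-off and adds a separate table for grade 3 and above, which indicates that the general tables were meant to cover all grades. No visible rule removes Grade 1 events.

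A reader might also infer that omitted events are moved into the non-TEAE group. They are not, because that group is described by onset date. Infusion-site reactions are a poor example of what could be lost, since SAP 7.1.8 gives them their own summary and listing with no significance filter. The open-label setting adds little: severity and causality are judged with the dose known too, there is no control arm, and no testing of safety data is planned.

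Finally, parts of Protocol 6.3.14.1.1 and 6.3.14.2.1 are redacted, and a criterion or a recorded item could lie there.

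All of this limits the consequence. None of it removes the qualifier from the two definitions or supplies a visible rule for applying it to non-laboratory AEs. If all grades were intended, the words serve no purpose.

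**Conclusion.** The point holds as a defect of definition. The stated TEAE rule is narrower than the AE definition, cannot be applied reproducibly from the visible text, and read literally can leave some in-window post-dose AEs out of both the TEAE tables and the non-TEAE group. Whether any would be lost depends on how the flag is programmed. The loss is none with a date-based flag, and an unknown share of mild events if the words are applied as a filter. Tables of serious events and of grade 3 or above have little to lose. Every AE would still be listed and would count in the all-AE summary.

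The conclusion assumes that the redacted text contains no criterion, assessor or data item for clinical significance of non-laboratory AEs. It is worth correcting before database lock because the TEAE set carries a primary endpoint and the correction is small.

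**What to change.** Delete the words *clinically significant* from the TEAE definition in SAP section 4, and from Protocol 6.3.14.1.1 at the next amendment. Define a TEAE as any AE, of any grade, that starts or worsens in intensity or frequency after the first dose, up to and including the +42-day follow-up visit. Keep clinical significance only where the protocol uses it as the threshold for calling a laboratory abnormality an AE.

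The cost is a few words in each document. On the visible text, the flag then needs only AE onset or worsening and dosing dates. TEAE counts may rise slightly compared with a version in which the qualifier was applied.
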